#### 5.5.2.2 Collection of blood sample

The on-duty Healthcare Assistant (HCA) or Phlebotomist at the NNUH; who will be taking approximately 4ml blood as part of the participant's routine clinical care (to test for inflammatory biomarkers), will be asked to obtain an additional 40 mL blood sample during the same procedure to minimize inconvenience to the participant. This additional 40 mL blood sample will be collected solely for the purpose of this study, and in the form of 2 x 10 mL whole blood (20 mL in Vacutainer EDTA tubes) and 2 x 10 mL serum (20 mL in Vacutainer SST tubes).

#### 5.5.2.3 Collection of 7-day food diary, baseline health and lifestyle questionnaire and clinical data

The participant's completed 7-day food diary will be collected, and any member of the Study Team will go through a baseline health and lifestyle questionnaire (Appendix 9) with the participant at this stage. No further 7-day food diaries will be provided to the participant for the purpose of this study. A methotrexate treatment record will be provided to the participant (Appendix 23) where they will record the dates and dosages of methotrexate taken. Participants will need to keep this document until they have completed the study, so it will be retrieved at the final study visit (6 month routine treatment review).

After the appointment, a member of the study team with appropriate access to NNUH hospital systems will obtain clinical data including DAS28-CRP (recorded by the clinician) using the Case Report Form (Appendix 11).

[figure not shown]
### 5.5.3 Third and fourth appointments: Routine Treatment Review

The following two data collection points will coincide with routine treatment review appointments organized as part of the participant's normal care pathway (at approximately 3 and 6 months from the NP appointment or time of commencing MTX/post-MTX).

The 3-month appointment will reflect the NP appointment in that another 40 mL blood sample will be taken for the purpose of this study by the on-duty HCA/Phlebotomist; as per Section 5.5.2.2, and the participant's stool sample will be collected from them as per Section 5.5.2.1. Clinical data will be recorded by a member of the study team with appropriate access to NNUH hospital systems using the Case Report Form (Appendix 11). Any member of the Study Team will go through another health

and lifestyle questionnaire with the participant, although this will be a shortened partial version of the questionnaire aimed at identifying changes (if any) from the NP appointment (Appendix 10). The participant will be provided with another stool collection kit for the final stool sample to be

**Figure 3:** Flowchart of involvement of participants in the study

brought to their next treatment review (at 6 months post-MTX, approximately 3 months after their 3-month treatment review).

At the 6-month treatment review, the participant's final stool sample will be collected as previously, any member of the Study Team will go through a final follow-up health and lifestyle questionnaire (Appendix 10) with the participant and their methotrexate treatment record (Appendix 23) will be collected. Clinical data will be recorded by a member of the study team with appropriate access to NNUH hospital systems using the Case Report Form (Appendix 11). No further blood samples will be taken for the purpose of this study at this 6-month treatment review. Following this final appointment, no further information will be required from the participant and their involvement with this study will end. Their routine care will continue as normal.

## 5.6 Withdrawal procedure

If at any point during the study the participant wishes to withdraw, they may do so without giving a reason and their clinical care and participation in future studies at QIB, UEA or NNUH will not be affected. The participant will be sent a withdrawal letter (Appendix 12) explaining this and thanking them for their participation so far. Any samples or data collected up to the point of withdrawal will be kept and used in the study.

The withdrawal letter (Appendix 12) will also be sent to participants if they need to be withdrawn from the study by a member of the study team due to meeting exclusion criteria; for instance, due to cessation of MTX therapy or starting MTX prior to collection of the first stool sample.

## 5.7 Data collection and storage

Data will be collected in the form of a health and lifestyle questionnaire (Appendix 9 and 10) and 7-day food diary (Appendix 8), in addition to clinical metadata collected by any member of the Study Team with the necessary access to hospital systems ([name], [name], [name]). Clinical data including DAS28-CRP, CRP, erythrocyte sedimentation rate (ESR), anti-cyclic citrullinated peptide (anti-CCP), rheumatoid factor, height/weight and Bristol stool score will be collected by means of a study-specific Case Report Form (Appendix 11).

All potentially patient-identifiable and other physical data (e.g. forms) will be stored in a locked file cabinet at QIB, with access restricted to study scientists. Patients will be provided with a unique patient identifier consisting of an unrelated sequence of numbers which does not contain any personal information (MyRA\_year\_month of consent\_participant number [MyRA\_18\_10\_01], and samples will be anonymized at the point of receipt using a suffix to this identifier (\_time point and sample type [stool or blood] e.g. S1 or B1 \_date sample taken [MyRA\_18\_10\_01\_S1\_251018]). Linked information will be kept in separate files from the personal information pertaining to each participant, and if the participant is also taking part in the NOAR study this information will include their unique NOAR identifier. The location of each sample in QIB (or later the NRP Biorepository) will be recorded. Any data electronically inputted or generated in relation to forms and samples will be stored in a secure (password-protected or encrypted) database on QIB computers.

### 5.7.1 Collection of disease activity variables

#### 5.7.1.1 DAS28-CRP

The DAS28 is a composite score made up of counts of the number of swollen (SJC) and tender (TJC) joints out of a total 28 measured, erythrocyte sedimentation rate (DAS28-ESR) or C-reactive protein (DAS28-CRP), and a health assessment questionnaire (patient global assessment of disease activity [PtGA], measured via a visual analogue scale [VAS]) filled in by the patient. While DAS28-ESR and

DAS28-CRP are often used interchangeably in clinical practice, DAS28-CRP will be used for this study; as ESR is not always measured in clinical laboratories.

DAS28-CRP is used by clinicians to monitor patient progress and inform treatment strategies, and will be recorded by the clinician at each routine appointment. DAS28-CRP in the participant's electronic or paper notes will be recorded by a member of the study team with appropriate access to hospital systems via the Case Report Form (Appendix 11). Should the DAS28-CRP not be recorded during a routine clinical appointment, each component of the DAS28-CRP is listed individually to enable calculation by the study team using the below equation:

$$0.56 \times \sqrt{TJC} + 0.28 \times \sqrt{SJC} + 0.36 \times \ln(CRP + 1) + 0.014 \times PtGA + 0.96$$

#### 5.7.1.2 Other measures of disease activity

Although DAS28-CRP is the standard measure used in medicine to measure RA disease activity, other measures may be used by some clinicians. Therefore another disease activity variable which we will record in this study via the Case Report Form (Appendix 11) is the Simplified Disease Activity Index (SDAI), which uses the same variables as DAS28-CRP but with the addition of provider global assessment of disease activity (PrGA). PrGA is a similar measure to PtGA and is also measured on a VAS, but is an indicator of the clinician's opinion on their patient's disease activity. The SDAI is calculated as a cumulative sum of SJC, TJC, PrGA, PtGA and CRP.

**Figure 4. Overview of data collection time points**

Activity	Pre-study	Week 0 (Early Arthritis Clinic)	Week 2-3 (Nurse Practitioner)	Week 12-15 (3 month Routine Treatment Review)	Week 24-27 (6 month Routine Treatment Review)
Identify suitable participant and send PIS and response slip	✓				
Telephone discussion to discuss study and confirm date and time of next appointment (on receipt of positive response)	✓	✓*			
Informed consent		✓	✓*		
Provide Fecotainer to participant		✓	✓	✓	
Provide 7-day food diary to participant		✓	✓*		
Provide methotrexate treatment record to participant			✓		
Stool sample and health questionnaire collected			✓	✓	✓

7-day food diary collected			✓	✓*	
Methotrexate treatment record collected					✓
Clinical data collected via case report form			✓	✓	✓
40 mL blood sample (20 mL serum, 20 mL whole blood)			✓	✓	

\*If participant is identified at the Early Arthritis Clinic, these activities will be carried out at this later stage.

## 5.8 Diet and lifestyle assessment

7-day food diaries have been provided by the European Prospective Investigation of Cancer (EPIC) study, are validated and approved for re-use in this study. [name] will be responsible for the data entry and analysis of these food diaries, for which expertise will be drawn from diet and nutrition researchers at UEA. Dietary analysis software such as Tinuviel (WISP) will be used for determination of micro/macronutrient intakes from food diaries, as it has been in previous studies. The specific diet components to be analyzed will be based on current known dietary risk factors for RA, including red meat, fatty fish (omega 3), and vitamin C intake. Other components to be investigated will be determined in an analysis of epidemiological data from the EPIC/NOAR link (participants in EPIC who are also registered with NOAR, for which there is historical 7-day food diary information available). Additional dietary components identified in association with methotrexate response from the EPIC/NOAR link data will be drivers for the analysis of food diaries in this study.

The health and lifestyle questionnaires are taken from the Microbiome of the Ageing Gut and its Effect on Cognition (MOTION) study, and have been approved for re-use in this study. The IRAS number for the MOTION study is 241617, and the ethical application is still in progress. The health and lifestyle questionnaire was reviewed by Patient Participation Groups (PPG) from four Norfolk GP sites. Twelve members from the four PPG groups returned comments on the questionnaire. Comments were noted and amendments made. The questionnaire consists of several questions related to factors which can affect microbiome composition, such as the use of over-the-counter or prescription drugs, living arrangements and recent travel. Recording these factors at baseline and changes at each subsequent time point will help account for confounding variables during the analysis of microbiome data.

## 5.9 Sample processing and analysis

### 5.9.1 Blood samples

#### 5.9.1.1 Collection and storage

Blood samples will be collected at the second and third appointments by the on-duty HCA or Phlebotomist at the NNUH Rheumatology Department who will be taking blood samples as part of the participant's routine clinical care. A total of 80 mL blood will be taken for the purpose of this study at the second and third appointment (pre- and post-MTX), in the form of 2 x 10 mL Vacutainer SSTs and 2 x 10 mL Vacutainer EDTA tubes. Serum samples will be aliquoted and frozen in a -20°C freezer, whereas whole blood samples will be processed to isolate PBMCs which will be stored in cryovials in liquid nitrogen until further analysis can be carried out. Both samples will be stored at QIB (within a maximum of 1 hour after receipt) for the duration of the study and will be transferred to the NRP Biorepository at the end of the study for long-term storage.

### 5.9.1.2 Immunological analyses

Serum and whole blood samples will be used in immunoassays currently being developed at QIB. The serum assay will involve enzyme-linked immunosorbent assays (ELISA) in which systemic antibodies against components of the participant's own microbiota (derived from their stool sample) are detected. This analysis will identify if the participant has systemic immunity against their own gut microbiota, which could be an indicator of a "leaky gut". PBMCs will be isolated from whole blood samples and frozen for future use in cellular assays for immune reactivity to commensal microbes; for instance, using proliferation assays and cytokine production assays. Together, these assays will provide information on systemic immune reactivity towards components of commensal microbes, giving an indicator of intestinal permeability and the ability of these microbes to elicit immune responses in the host. Changes to the participant's immune reactivity against their own gut microbes may occur with treatment (for instance if there was increased intestinal permeability prior to treatment which resolved with MTX), which will also be assessed in this study.

## 5.9.2 Stool samples

### 5.9.2.1 Collection and storage

Stool samples will be collected by the participant and received by any member of the Study Team at the second, third and fourth appointments. These samples will either be delivered to the NNUH by the participant at their routine appointment or collected by a member of the study team from their home a day either side of this appointment. Collection by the study team from the participant's location will have been organized between the participant and study team to arrange a suitable time. Each stool sample will be separated into aliquots and frozen at -80°C in a QIB freezer until further analysis can be carried out. This will be done as soon as possible after collection of the fresh sample (within a maximum 1 hour after receiving the sample), to avoid unwanted changes to the microbial communities present in the sample. Any remaining original sample will be discarded, and at the end of the study stool samples left over will be transferred to the NRP Biorepository for long-term storage.

### 5.9.2.2 Shotgun metagenomic sequencing

Total microbial DNA will be extracted from stool samples, quantified and sent to Novogene (Hong Kong) for shotgun metagenomic sequencing on the Illumina platform (insert size, 300bp; paired-end read length, 150bp; depth, 10GB data per sample). The resulting sequencing data received from Novogene will be used to identify the  $\alpha$ -diversity (Shannon Index) and bacterial composition and functional profiles in the stool samples. The raw sequences will also be used to identify viral sequences, using a pipeline currently being developed at QIB. Correlations will be drawn between  $\alpha$ -diversity (Shannon Index) and change in DAS28-CRP to answer the primary research aim. Various statistical analyses (see Statistical Methods) will be carried out to determine the diversity (e.g. Shannon index, Bray-Curtis dissimilarity) and differential abundance of microbial genera between responders and non-responders to MTX; which will inform on the reliability of microbiome parameters as predictors of MTX response. This analysis will be carried out by [name] with the support of QIB Bioinformaticians.

## 6 Dissemination of findings

Data generated from this study will be anonymized and published as part of a postgraduate thesis and research journal articles. The data may also be presented in anonymized form at conferences. At the end of the study, a brief, lay summary of the findings of the study will be posted to participants on QIB headed paper, meeting the HRA transparency requirements under the new

General Data Protection Regulation (GDPR) legislation. Anonymized datasets will be kept indefinitely and available to other researchers to comply with journal requirements when required.

## 7 Statistical methods

### 7.1 Sample size calculations

Sample size calculations were carried out by [name], a QIB statistician. Previous studies suggest that change in DAS28 score in response to treatment has a standard deviation of 1 to 1.3 points. The minimum clinically relevant difference in DAS28 has been reported in two different studies as 1-1.2 points.

Hence, to detect a clinically relevant difference in DAS28 we will aim to recruit enough participants to estimate an effect size of one standard deviation in the outcome per two standard deviations in Shannon index, corresponding to a correlation coefficient of 0.5, typically considered a large effect. This will require 30 subjects to complete the study (true power=82.5%, size=0.05), hence our target sample size for recruitment is 35, allowing for 5 participants to drop-out of the study. Using the change score from baseline to the mean of two follow-up responses as the primary outcome will slightly improve the power of the study but it is difficult to know by how much without prior information on the longitudinal variation of DAS28. Power calculations were conducted using the *pwr* package in R.

Multivariate analyses linking detail of the structure and composition of the microbiome to outcomes are purely exploratory and will be reported as such.

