### 7.2 Statistical methods for the analysis of study data

#### 7.2.1 Correlating microbiome parameters with treatment outcome

Spearman's correlation coefficient will be used to identify statistically significant associations between (continuous variables) Shannon index at baseline and change in DAS28-CRP from baseline to 3 months post-MTX. In addition, Shannon index and other microbiome characteristics such as taxa and gene abundance will be analysed for covariation with other clinical metadata (CRP, anti-CCP, RF), also using Spearman's correlation coefficient. The predictive capability of the microbiome for MTX response will be assessed by generation of a cross-validated predictive model, using a machine-learning R statistical package such as *randomForest*.

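### Protocol section 7.1 labels 82.5% as power for a clinically relevant DAS28 difference, but it is power for a correlation of 0.5; the two agree only if that difference equals the SD

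*Protocol*

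**What the plan says.** Protocol section 7.1 (Sample size calculations) sets out two literature inputs. On variability: "change in DAS28 score in response to treatment has a standard deviation of 1 to 1.3 points". On relevance: "The minimum clinically relevant difference in DAS28 has been reported in two different studies as 1-1.2 points".

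It then draws an inference from these. The study aims, "to detect a clinically relevant difference in DAS28 we will aim to recruit enough participants to estimate an effect size of one standard deviation", and the effect is specified as "one standard deviation in the outcome per two standard deviations in Shannon index, corresponding to a correlation coefficient of 0.5". The result is: "This will require 30 subjects to complete the study (true power=82.5%, size=0.05". Recruitment follows from that: "our target sample size for recruitment is 35, allowing for 5 participants to drop-out of the study". On software: "Power calculations were conducted using the *pwr* package in R".

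Section 7.2.1 names the primary test, which relates baseline Shannon index to change in DAS28-CRP at 3 months: "Spearman's correlation coefficient will be used to identify statistically significant associations".

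Section 7.1 does not say that the relevant difference is being taken as equal to one SD. It gives no power for any other pair of values within its two ranges.

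**The concern.** The passage starts with a difference in DAS28 points and ends with a difference in SD units, and it treats the second as following from the first. They are the same quantity only if the SD equals the relevant difference. Both inputs are given as ranges, and the ranges differ, so the conversion is an assumption that is neither stated nor tested.

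What is at stake is how the power figure is read. As worded, 82.5% describes the chance of finding an association that matters clinically. Someone interpreting a null result could lean on that description. If the SD of change is near the top of the cited range and the effect near the bottom of the relevant range, the chance of detection is little better than even. Spearman's coefficient has no units, so the primary result alone would not show how the estimate compares with 1 to 1.2 points.

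**Working it through.** **Inputs (all from Protocol section 7.1 except the last)**

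- SD of DAS28 change, *s*: 1 to 1.3 points
- Relevant difference, *d*: 1 to 1.2 points
- Contrast: two SDs of the Shannon index
- n = 30 completers, significance level 0.05; sidedness not stated
- Planned test: Spearman (section 7.2.1)

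**Step 1. Reproduce the stated figure.** The method for a correlation in the pwr package uses Fisher's z with a small bias term and a critical value from the t distribution:

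- r_crit = √[t² / (t² + n − 2)], where t is the 97.5% point of t on n − 2 degrees of freedom
- z_r = atanh(r) + r / [2(n − 1)]
- power ≈ Φ{[z_r − atanh(r_crit)] × √(n − 3)}, plus a negligible opposite tail

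With n = 30 and r = 0.5, two-sided, this gives 82.50%. A simulation of the Pearson test (50,000 runs) gives 82.5%. The one-sided version gives 89.5%, so the protocol's figure is two-sided. It is reproduced exactly.

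**Step 2. Convert points to a correlation.** Under a linear relation, moving two SDs along the Shannon index shifts the expected outcome by 2 × r × s points. Setting this equal to *d* gives

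r = d / (2s).

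So r = 0.5 corresponds to d = s: 1.0 point if the SD is 1.0, and 1.3 points if the SD is 1.3.

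**Step 3. Power at n = 30 over the protocol's own ranges** (Step 1 formula, two-sided 5%; implied r in brackets)

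| SD of change | d = 1.0 | d = 1.1 | d = 1.2 |
|---|---|---|---|
| 1.0 | 82.5% (0.500) | 90.3% (0.550) | 95.5% (0.600) |
| 1.15 | 69.0% (0.435) | 78.4% (0.478) | 86.2% (0.522) |
| 1.2 | 64.7% (0.417) | 74.2% (0.458) | 82.5% (0.500) |
| 1.3 | 57.0% (0.385) | 66.2% (0.423) | 74.9% (0.462) |

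The top-right value is 95.46% before rounding, hence 95% to the nearest whole number.

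- The midpoints of both ranges (d = 1.1, SD = 1.15) give 78.4%, about four points below the stated figure.
- In the 1-point column, 82.5% is the maximum, reached only at the smallest cited SD.
- In the SD 1.3 row, the maximum is 74.9%.
- Keeping 82.5% power would take 54 completers at r = 0.385, 36 at r = 0.462 and 20 at r = 0.6.

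**Step 4. The planned test.** The table shows Pearson power, which is what pwr computes. Simulated Spearman power at n = 30, assuming bivariate normality, is about 52% at r = 0.385, 77% at r = 0.5 and 93% at r = 0.6. The conversion in Step 2 concerns the underlying linear effect and does not depend on the test. The power percentages do.

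**The case against.** The calculation itself is sound. Section 7.1 states the standardised target openly, gives r = 0.5 and calls it a large effect, so a careful reader can see what 82.5% refers to. The two ranges overlap, and treating both as about one SD is a common simplification of uncertain inputs. This stands: there is no arithmetic error here.

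The 57% and 95% figures each pair opposite ends of the two ranges, and the central value is much closer to the stated one. One of the cited studies is a source for both the SD and the relevant difference, so the two may move together. The documents do not say which value comes from which source, so the 57% corner may not be a real pairing. This also stands, and it is why the mid-range value belongs beside the range.

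Three stronger readings are tempting, and the documents do not support them:

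- **The study is underpowered.** Power is above 82.5% wherever the relevant difference exceeds the SD, and reaches 95% at one corner.
- **82.5% always refers to a difference larger than the relevant one.** One SD exceeds the whole 1 to 1.2 range only when the SD is above 1.2. Between 1.0 and 1.2 it lies within that range.
- **The protocol claims that a null result would exclude a relevant association.** It makes no such claim. That is a risk of the wording, not something the plan says.

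The objection does not rescue the inference in section 7.1. Naming r = 0.5 does not turn it into the relevant difference, and the midpoint pair already falls below 80%. Nor is this a detail left to an analysis plan: the inputs and the conclusion drawn from them stand together in the protocol.

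**Conclusion.** The point holds as a mislabelled power figure. The 82.5% is correct for a Pearson correlation of 0.5 with 30 completers and a two-sided 5% test. As power for a clinically relevant difference it is correct only where that difference equals the SD. On the cited ranges the corresponding figure is about 78% at the midpoints, with a range of 57% to 95%. It is at most 82.5% for a 1-point difference and at most 75% if the SD is 1.3.

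This rests on the protocol's own contrast of two SDs of the Shannon index, a linear relation, a two-sided test (inferred from the match to 82.5%) and the two ranges taken at face value. The Spearman figures also assume bivariate normality. Neither the sample size nor the primary test is shown to be wrong.

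**What to change.** Restate section 7.1 along these lines:

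> *Thirty completers give 82.5% power (Pearson, two-sided 5%) for a correlation of 0.5, which corresponds to 1.0 to 1.3 DAS28 points per two SDs of the Shannon index, depending on the SD of change. For the cited relevant difference of 1 to 1.2 points, power is about 78% at mid-range values (range 57% to 95% over SDs of 1 to 1.3). The planned Spearman test has somewhat lower power: under bivariate normality, about 77% at a correlation of 0.5, with a range of about 52% to 93%.*

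Optionally, as a supportive output, report the fitted slope in DAS28-CRP points per two SDs of the Shannon index with its 95% confidence interval, so that the result can be set against 1 to 1.2 points. This could equally sit in the analysis plan, and the rank-based primary test stays as it is.

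The cost is a change of wording and, if adopted, one extra line of output. The stated power becomes slightly less favourable. No extra patients are needed.

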### 3 Hypothesis

A single microbiome parameter ( $\alpha$ -diversity, microbial diversity measured by Shannon index) in treatment-naïve early RA patients positively correlates with MTX response at 3 months (measured by change in DAS28- CRP) and can be used to predict treatment response in these patients.

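### The 82.5% power in Protocol 7.1 belongs to a two-sided Pearson test; the Spearman test planned in 7.2.1 has about 77% under bivariate normality

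*Protocol*

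**What the plan says.** Section 7.1 sizes the study to estimate "an effect size of one standard deviation in the outcome per two standard deviations in Shannon index", described as "corresponding to a correlation coefficient of 0.5, typically considered a large effect". It then states "This will require 30 subjects to complete the study (true power=82.5%, size=0.05"), and names the R package *pwr* as the source of the calculation. It does not say which correlation coefficient is meant or whether the test is one- or two-sided. Five further recruits, making 35, are set aside for drop-out.

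Section 7.2.1 names the analysis. Spearman's "correlation coefficient will be used to identify statistically significant associations between" two continuous variables, "Shannon index at baseline and change in DAS28-CRP from baseline to 3 months post-MTX". This is the association in the hypothesis of section 3, which is worded directionally: diversity "positively correlates with MTX response at 3 months".

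**The concern.** The power statement and the planned test refer to different statistics. One SD of outcome per two SDs of Shannon index is a standardised regression slope, so the 0.5 is a Pearson correlation, and a standard power calculation for a correlation coefficient is a Pearson calculation. The test in 7.2.1 is rank-based. When the data are close to bivariate normal, a rank correlation test has less power than the Pearson test on the same data, and section 7.1 neither mentions this nor adjusts for it.

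A reader will take 82.5%, printed to three figures and labelled as true, to be the power of the primary analysis. In a study of 30 people, sized for an effect that the protocol itself calls large, that figure is the main guide to interpreting a null result. Under bivariate normality the chance of missing the design effect is about 23% (100 − 77), not 17.5% (100 − 82.5).

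**Working it through.** **Inputs from the protocol.** n = 30 completers, correlation r = 0.5 and size 0.05 (section 7.1); Spearman test (section 7.2.1). Sidedness is not stated, so both versions are computed.

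**Step 1: reproduce the printed figure.** The Pearson power formula takes the critical correlation r_c from the t distribution on n − 2 = 28 df and works on Fisher's z scale with the small-sample bias term:

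- Power ≈ Φ{[atanh(r) + r/(2(n − 1)) − atanh(r_c)] × √(n − 3)}; the opposite tail is negligible.
- Two-sided: t = 2.048, so r_c = √(2.048² / (2.048² + 28)) = 0.361 and atanh(r_c) = 0.3780.
- atanh(0.5) + 0.5/58 = 0.5493 + 0.0086 = 0.5579.
- (0.5579 − 0.3780) × √27 = 0.935, and Φ(0.935) = **0.825**.
- One-sided: t = 1.701, r_c = 0.306, atanh(r_c) = 0.3162; (0.5579 − 0.3162) × √27 = 1.256, and Φ(1.256) = 0.895.

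The printed 82.5% is therefore the two-sided Pearson power. The one-sided version would have been 89.5%.

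**Step 2: power of the planned test.** Assumption, not in the protocol: bivariate normal data with Pearson r = 0.5. The population Spearman coefficient is then (6/π) × arcsin(0.5/2) = 0.483. Power was found by simulating 400,000 samples per setting, two-sided 0.05, with the t-based critical value of 0.361 at n = 30.

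| Setting, n = 30 | Pearson test | Spearman test |
|---|---|---|
| No correlation (type I error) | 5.0% | 5.1% |
| Pearson r = 0.5 | 82.7% | **77.2%** |
| Spearman 0.5, i.e. Pearson 2 sin(π × 0.5/6) = 0.518 | 85.7% | 80.5% |

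With a slightly stricter critical value of 0.362 the middle Spearman figure is 77.0%. The Spearman test holds its size, so the loss of about 5 points does not come from a conservative cut-off.

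**Step 3: what the gap means in participants.** Under the same assumption with Pearson r = 0.5, Spearman power is 78.7% at n = 31, 80.0% at 32, 81.4% at 33, 82.6% at 34 and 83.7% at 35. The printed power is reached with about 34 completers.

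**Step 4: sensitivity to shape.** The protocol gives no distribution for either variable, so the shapes below are assumptions. Outcome = 0.5 × predictor + √0.75 × error, both standardised; n = 30; two-sided; 200,000 samples each.

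| Predictor | Error | Spearman power |
|---|---|---|
| Normal | t with 5 df / Laplace / gamma(2) | 84% / 85% / 86% |
| Left-skewed gamma(4) | Laplace / gamma(2) | 82% / 83% |
| Left-skewed gamma(4) | Normal | about 73.5% |
| t with 5 df | Normal | 71% |
| Laplace | Normal | 69% |

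Heavy-tailed or skewed errors favour the rank test. A heavy-tailed or skewed predictor with normal errors works against it.

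**The case against.** The best case for leaving 7.1 alone has five parts.

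- **The 77% depends on the model.** Bivariate normality is the case in which a rank test is least needed, and the sensitivity range of about 69% to 86% includes 82.5%. This stands as a limit on the size and direction of the gap. It does not rescue the label: 82.5% was computed for a test that the plan does not use.
- **Sidedness is open.** Section 7.2.1 states none and the hypothesis is directional; a one-sided 0.05 Spearman test would have about 86% power under the same assumptions. But 82.5% reproduces only as two-sided, so the like-for-like comparison is two-sided. The protocol should say which it intends.
- **Using Pearson power for a Spearman test is a familiar planning approximation,** and 7.1 discloses the software, r, n and size. That would be acceptable if it were presented as an approximation, but it is not.
- **There is slack.** If all 35 recruits completed, Spearman power would be about 84% under normality. Section 7.1, however, reserves those five for drop-out and ties the power to 30 completers.
- **Averaging two follow-ups would add power.** Section 7.1 raises this but says the gain is hard to know, and the outcome tested in 7.2.1 is the change to 3 months. That difference in outcome is a separate inconsistency and does not supply the missing power.

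**Conclusion.** The concern holds: the power statement is wrong as written. The printed 82.5% is the two-sided Pearson power at r = 0.5 and n = 30, and it is not the power of the Spearman test that the protocol plans. With a two-sided test, bivariate normality and a Pearson correlation of 0.5, the planned test has about 77% power, roughly 5 points less. Reading 0.5 as the Spearman coefficient gives about 80.5%, still below the printed value. Without normality the true figure may lie on either side of 82.5%.

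The consequence is limited. The protocol states no target power, so this does not show that 30 completers are inadequate. It is worth correcting because it is the only power figure given for the primary analysis.

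**What to change.** Change the wording in section 7.1 only.

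1. After the correlation of 0.5, say which coefficient is meant. The SD-per-SD definition implies Pearson.
2. Replace the bracketed power statement with: *(power 82.5% for a two-sided Pearson test, size=0.05; about 77% for a two-sided Spearman test, the coefficient planned in 7.2.1, assuming bivariate normality and a Pearson correlation of 0.5)*. If 0.5 is meant as the Spearman coefficient, the second figure becomes about 80.5%.
3. State in 7.2.1 that the test is two-sided, if that is the intention. If a one-sided test is intended, both power figures must be recomputed on that basis.

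The cost is a sentence or two. The 30 completers, the recruitment aim of at least 35, the Spearman test, the endpoint and all procedures can stay. The authors would have to accept a quoted power about 5 points lower under normality.
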